Outcomes will be collected in the EHR at baseline and 3-month follow-up and for a subset of Veterans surveys will be administered at baseline with follow up points at 3, 6, 9, and 12 months. The primary outcomes (PROMIS pain interference and physical function) and secondary outcome (PROMIS sleep quality) will be captured in templated progress notes in the VA medical record for participants (n = 1,680) using PROMIS short form instruments (4 items per scale). A subset of these same participants (n=848) will be consented for the additional survey data collection. These additional data will be used in the secondary and exploratory analyses; and the measures include more detailed patient reported outcomes on pain associated distress, physical function, and health care utilization as well as longer term follow-up.

Care Pathways and Duration

The Integrated Care Pathway (ICP) includes both on-site physical therapy (PT) services (delivered by PT providers at each participating VA clinic) and centrally-delivered services via telehealth. The ICP will be initiated by a referral from a provider at a participating primary care clinic. The first step of the ICP is contact by the central delivery provider to explain the ICP, determine preferences in delivery mode for centrally-delivered services (telephone vs video) and initiate onsite PT services. Onsite PT services will include a physical examination, and pain modulation treatment as determined by the provider that could include manual therapy or electrotherapy and capture of baseline data on pain and function. This first step will consist of a maximum of 2 on-site PT visits and it will take 2 weeks. The second step of the ICP will last 6 weeks, with patients receiving telehealth (i.e. telephone or video) calls for home physical activity instruction. The calls are will be conducted by centrally located Durham VA providers.

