The third step of the ICP is referral back to the onsite PT after completion of the 6 weeks of physical activity instruction for 1 visit consisting of additional pain modulation treatments (if needed) and completion of a simple 9-question risk stratification tool (Start Back Screening Tool (SBST)). The SBST will be used to identify at higher risk for developing chronic or persistent back pain. Patients scoring as 'low risk' on the SBST are discharged from PT services, and the ICP will end with notification to the primary care clinic. Those patients scoring 'medium or high risk' on the SBST will receive 6 more weeks of ICP care consisting of weekly calls (telephone or

video) from providers at the Durham VA focused on psychological and behavioral activation components, consistent with what can be delivered by a physical therapist. This third and final step of the ICP will consist of 6 treatment sessions over 6 weeks, but only for those that have been identified as medium or high risk on the SBST.

The Coordinated Care Pathway (CCP) involves use of existing non-pharmacological services available at participating VAMCs. The CCP will be initiated by a referral from a participating primary care clinic. The first step of the CCP is telephone or video (depending on availability and common practices at the site) contact with a pain navigator. The pain navigator will be an on-site provider trained to elicit patient preferences for non-pharmacological treatments and is knowledgeable in current recommended treatment guidelines for low back pain. The pain navigator will engage in a shared-decision making process with patients to determine the appropriate nonpharmacological, guideline supported VA service for their LBP. The pain navigator will coordinate consultation of these services to increase the likelihood of receiving the interventions. Consistent with the pragmatic nature of this trial, there will be no control of the duration or intensity of treatment received in the CCP. However, we expect that receiving the first recommended service will take approximately 6 weeks. If an additional service is needed, the above process will be repeated with the pain navigator to gain referral to another non-pharmacological service. This is expected to take another 6 weeks. If additional services are requested after the second consult with the pain navigator the patient will be referred back to the primary care clinic for additional medical examination.

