4.1 Participant Inclusion Criteria

At the level of the individual, participant eligibility criteria are intentionally broad in keeping with the pragmatic nature of this trial. Eligibility criteria will be applied equally to and are appropriate for individuals seeking care at any of the clinical sites. Site training will include instruction in the referral criteria so that providers have consistency in the selection of participants for the care pathways (see below). Our intent is to: 1) examine the care pathways in the way they would be used in clinical practice; and 2) maximize diversity and the potential to generalize the findings from this trial.

Referral Criteria (part of site training and used by providers for pathway determination)

1. LBP that is localized or radiating
 - Localized = symptoms reported in the T12 to S5 region only, occurring unilaterally or bilaterally

- Radiating = localized symptoms reported in the T12 to S5 region, occurring unilaterally or bilaterally and radiating symptoms to the buttocks, thigh, or lower leg
- 2. LBP that is appropriate for conservative care
 - No history of recent spinal trauma or surgery (i.e. past 3 months)
 - No signs or symptoms suggestive of spinal fracture, tumor, or infection

Specific inclusion criteria for inclusion in the analyses are listed below.

Inclusion Criteria (must meet all)

1. Age ≥ 18
2. Seeking care for LBP with or without radiating symptoms from a participating VA primary care clinic
3. Provider determines LBP is appropriate for conservative management
4. Referred to integrated ICP pathway or CCP pathway by participating clinic provider

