4.2 Participant Exclusion Criteria

Narrower eligibility criteria would exclude a significant number of patients with LBP resulting in limited application of examined care pathway models. Some patients will not meet clinical criteria for all treatments within each pathway; however, they will be included in the evaluation to be consistent with our pragmatic goals of determining the average treatment effect of each arm for patients with LBP when receiving routine clinical care. All adult subjects (not referred for hospice or palliative care) that are enrolled in a participating VA primary care clinic and are referred to one of the LBP pathways will be eligible for the main analysis.

Exclusion Criteria (if meet any)

1. Receiving or referred for hospice/ palliative care (defined by encounter codes and CPRS consults)
2. No documented phone number in the electronic health record.

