4.3 Study Enrollment Procedures for Outcome Collection

Enrollment procedures. We anticipate total sample size of 1,680 Veterans for the administrative sample (main analysis). For these participants, data will be obtained from VA administrative and electronic health records.

We will recruit a subset of Veterans (n=848) to participate in a series of telephone interviews. The selection of this subset is described in the subsequent section (Screening, Informed Consent, Baseline Data Collection). Because these participants will be asked to provide additional information over and above what is collected and stored in the electronic health record as part of routine clinical care, we will seek informed consent for participation in this portion of the study, using the following procedures. The additional inclusion/exclusion criteria for the telephone subset are:

Inclusion Criteria for Telephone Survey Subset (must meet all)

1. Valid phone number in medical record
2. Able and willing to provide informed consent

Exclusion Criteria for Telephone Survey Subset (if meet any)

1. Currently in institutional care (nursing home or hospital).
2. Cognitive impairment or dementia (identified via ICD diagnosis codes or PCP note in previous 2 years) or lack decision-making capacity, documented in the medical record.
3. Serious mental illness defined as diagnosis of schizophrenia, bipolar disorder, psychiatric hospitalization in the previous year or current high-risk suicide flag in their CPRS medical record.
4. Unable to communicate on the telephone, or no telephone access for duration of study

Opt-out letter and enrollment over the telephone. At the beginning of the study, centrally located Durham VA study staff will generate an opt-out letter signed by the research team that will be mailed to all potentially eligible patients enrolled in participating VA primary care clinics. The letter will describe the study and include an “opt-out” phone number if they do not wish to be contacted further. We will also include opt-out information on printed clinical program brochures that providers give patients in clinic at the time of referral.

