9.3 Definition of Populations

As this is an embedded pragmatic trial, all adult subjects that present to clinics with LBP and are referred to one of the two arms of the trial with initial contact with pain navigator or central delivery for data collection will be eligible for the primary analysis as part of the administrative sample. A subset of these Veterans will be enrolled as research subjects so that more detailed research data can be collected at regular intervals for follow up. For this subgroup, equivalent numbers of Veterans with LBP will be enrolled at each clinic.

The primary analyses will be conducted on an intention-to-treat basis; patients will be analyzed in the group to which they were randomized, regardless of intervention adherence, using all available data. The main conclusions drawn from this trial will be based on the pre-specified hypotheses outlined below and will be tested with two-sided p-values at the standard 0.05 level, except where noted due to multiple primary outcomes. For all study outcomes, we will interpret differences between groups over time with reference to prior literature regarding clinically meaningful changes. Results from exploratory analyses will be interpreted with appropriate consideration for their exploratory nature. Statistical analyses will be performed using the latest release of SAS for Windows (Cary, NC) and R software.

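### Section 9.3 makes initial contact a condition of an analysis it calls intention-to-treat, in conflict with sections 4.1 and 4.2, and carries that condition over to record-based outcomes that do not need it

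*Combined protocol and SAP*

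**What the plan says.** **Eligibility.** The last inclusion criterion in section 4.1 is "Referred to integrated ICP pathway or CCP pathway by participating clinic provider". Section 4.2 states that adults at participating clinics who "are referred to one of the LBP pathways will be eligible for the main analysis", apart from hospice or palliative patients. Its one criterion related to reaching the patient is a records check: "No documented phone number in the electronic health record". Neither section requires that contact take place. Section 4.3 treats the administrative sample, projected at 1,680, as the main-analysis sample.

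**Analysis population.** Section 9.3 admits to the primary analysis adults with low back pain "referred to one of the two arms of the trial with initial contact with pain navigator or central delivery for data collection". It then says the analysis is intention-to-treat, with patients "analyzed in the group to which they were randomized, regardless of intervention adherence, using all available data".

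**What contact is.** The Précis says: "The first step of the ICP is contact by the central delivery provider to explain the ICP". For the other arm it says: "The first step of the CCP is telephone or video", meaning contact with a pain navigator. ICP contact comes from central Durham VA staff and CCP contact from an on-site navigator. Section 9.2.1 says delivery personnel are not blinded to clinic assignment.

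**Record-based outcomes.** Sections 9.1 and 9.5.2 place opioid use and utilization on the administrative sample (n=1680); section 9.6 refers to all eligible subjects. Section 6.2 counts imaging from referral and ED visits from enrollment. Section 9.5.2 counts both from referral, and measures opioid use at baseline and 12 months later.

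**The concern.** Clinics are randomised first. Patients are then referred, and only after that contacted. A rule that keeps only contacted patients selects on something the assigned pathway can influence: who calls, from where, how soon, and how the pathway is described. If contact succeeds for different kinds of patients in the two arms, the contacted groups are not comparable in the way the clinics were at randomisation. The label in section 9.3 says adherence plays no part in the analysis set, yet in CCP failing to take up the navigator referral is itself scored as non-adherence (0/1 in Table 3).

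Two things are at stake. A reader of the PROMIS result would take it as covering all referred patients when it covers those who were reached. And for opioid, imaging and ED outcomes, patients whose records are available would be dropped for no gain in data. Two analysts working from sections 4.2 and 9.3 could also build different datasets.

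**Working it through.** **1. The plan's own figures.** 84 per clinic at follow-up with 20% attrition gives 84/(1 − 0.20) = 105, and 16 × 105 = 1,680. For Table 8, with two-sided alpha 0.025, 90% power, over-time correlation 0.50, 8 clinics per arm, m = 84 and 16 − 2 − 5 = 9 degrees of freedom:

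- multiplier t(0.9875) + t(0.90) = 4.068
- SE = √{4[(1 − ICC)(0.5) + m·ICC(0.5)]/(8m)}
- detectable effect 0.300 / 0.362 / 0.504 at ICC 0.01 / 0.02 / 0.05, against the stated 0.30 / 0.36 / 0.50.

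The figures reproduce.

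**2. The population rules side by side.**

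| Section | Last step required |
|---|---|
| 4.1, 4.2 (main analysis) | referral |
| 5.2 Adherence Assessment | referral (includes patients who attended no session) |
| 9.3 (primary analysis) | referral and initial contact |
| 9.1, 9.5.2 (opioid, imaging, ED) | inherited from the administrative sample |
| 9.6 (same outcomes) | inherited from whichever eligibility rule applies |

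The adherence analysis therefore counts patients whom section 9.3 removes.

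**3. The start dates side by side.**

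| Outcome | Section 6.2 | Section 9.5.2 |
|---|---|---|
| Imaging | referral | referral |
| ED visits | enrollment | referral |
| Opioid use | not given | baseline, no date attached |

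Section 8 links enrollment to referrals, whereas section 9.3 uses enrolled for the survey subset. Aim 2 in section 9.6 anchors prior opioid exposure at pathway entry.

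**4. How many patients the rule could remove.** No contact rate c is given, so c is assumed. If 1,680 are referred, 1,680 × (1 − c) gives 168, 336 and 504 for c = 0.90, 0.80 and 0.70.

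**5. How far two analyses could diverge.** Let d be the mean outcome in uncontacted minus contacted patients within an arm. The all-referred mean in an arm equals the contacted mean plus (1 − c)d. The all-referred ICP − CCP difference minus the contacted-only difference is therefore

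(1 − c_ICP)d_ICP − (1 − c_CCP)d_CCP,

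which is (c_CCP − c_ICP)d when d is equal in both arms. Every input below is assumed.

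- Chronic opioid use at 12 months, contact gap 10 to 20 percentage points, d of 5 to 10 percentage points: 0.10 × 5 = 0.5 up to 0.20 × 10 = 2.0 percentage points, in either direction.
- Equal contact of 80% in both arms, d of 10 in ICP and 5 in CCP: 0.20 × 10 − 0.20 × 5 = 1.0 percentage point. Equal contact rates alone do not guarantee agreement.
- Equal contact and equal d: zero.

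**6. PROMIS.** The baseline score is taken at the initial contact, so a patient never contacted has essentially nothing to contribute to a likelihood model on available data. Widening the definition changes the description of that estimate far more than its value.

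**The case against.** The best defence is that section 9.3 describes contact as serving data collection, and that without it there is no PROMIS score to analyse. For the primary outcomes this largely stands: the restriction is a fact about the data, and only the label needs correcting. There are mitigating features too. Treating providers have no training in the other pathway (section 6.3), initial contact is followed through biweekly reports (section 6.1), and adherence is described among all referred patients. None of these makes the contacted groups comparable between arms, and the defence does not reach outcomes drawn from existing records.

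Four stronger readings are tempting, and the documents do not support them.

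- *Non-contact is scored as non-adherence in both arms.* This holds only for CCP. The eight ICP items begin with the physical therapy referral; the central-delivery call is not among them.
- *All the start dates conflict.* Imaging is dated from referral throughout. The opioid baseline is unanchored rather than contradictory. The ED conflict is softened by section 8, though not removed. Figure 4 and the appendices are not in the text available for review and might fix an index date.
- *The sample size is wrong, because section 8 counts 105 referred and Table 8 counts 105 at baseline.* Nothing says that non-contact comes on top of the 20% attrition. Even if it did, at an assumed 80% contact m = 67.2 gives 0.320 / 0.378 / 0.515, close to the Table 7 row with 79 at baseline (0.32 / 0.38 / 0.52).
- *Sections 9.5.2 and 9.6 name two different populations for the secondary outcomes.* They agree once one eligibility rule applies; the problem is inherited from sections 4.2 and 9.3.

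**Conclusion.** The inconsistency is established from the text: sections 4.1 and 4.2 stop at referral, section 9.3 adds a post-randomisation pathway step, and the plain intention-to-treat label does not fit the population that results. For opioid, imaging and ED outcomes the restriction is unnecessary. The ED clock needs one wording, and the opioid baseline needs a date.

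A reader might infer that the PROMIS comparison is biased towards one arm. The documents do not show that: they give no contact rates, no arm difference in contact and no outcome difference by contact, so sign and size are unknown and zero is possible. The 168 to 504 patients and the 0.5 to 2.0 percentage points in the working show scale under assumed inputs; they are not estimates. This should be corrected before analysis, but it does not threaten the design or any stated power figure.

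**What to change.** 1. In sections 4.1, 4.2 and 9.3, define the intention-to-treat population as all eligible referred patients. Analyse opioid, imaging and ED outcomes on it, with the referral date as the single index date. In section 6.2, replace the enrollment clock for ED visits with referral; in section 9.5.2, tie the opioid baseline to referral.
2. Keep the PROMIS mixed model on available data as planned, but describe it as conditional on initial contact (modified intention-to-treat).
3. Report the numbers referred and contacted, by arm and by clinic.
4. State that this removes selection by contact but not selection by referral, since referral also follows clinic randomisation.

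Imputing PROMIS scores for patients never contacted is optional.

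The cost is SAP wording, one flow table and a minor extension of the record-based analyses. No new collection is needed: referrals and initial contacts are already tracked, and the adherence analysis already covers all referred patients. The drawback is that the record-based and PROMIS outcomes will rest on different populations, each of which must be clearly labelled.

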9.4 Interim Analyses and Stopping Rules

Interim analyses and stopping rules are not applicable to our embedded pragmatic trial.

9.5 Outcomes

9.5.1 Primary Outcome

Co-primary outcomes will be pain interference with normal activities and functional status, assessed by PROMIS Short Form scores collected in the EHR on the administrative sample (n=1680) at baseline and 3 months; 3 months is the primary outcome time point. For baseline and 3-month follow-up, we will rely on central delivery personnel and clinical providers in ICP and pain navigators in CCP to collect these data in the EHR via progress note templates to collect health factors relevant for the analysis for the PROMIS pain interference and functions scores (see Section 6). For the follow-up, a report will be generated every 2-weeks to evaluate which participants are due for the 3-month follow-up and the report will be sent to central delivery personnel or pain navigator for them to administer these measures (see outcome ascertainment study flow diagram in Figure 4. The window around the 3-month outcome assessment will be 1-month. If outcome assessment occurs outside of this defined window they will not be included in the primary analysis. Given that this is an embedded pragmatic trial the study team will monitor outcome ascertainment timing at each participating clinical site to trouble-shoot any problems or issues to circumvent loss of outcome data.

9.5.2 Secondary Outcomes

Secondary outcomes of PROMIS sleep, opioid use, and utilization will also be obtained administratively on the full administrative sample (n=1680). As previously described for the primary measure PROMIS sleep will be collected at the same times as the primary outcomes in the EHR (see Section 6). Opioid use will be defined at baseline and then at 12 months later using the PMC3 provided definition. For imaging and ED utilization, we will measure use for the 12 months following referral.

9.6 Data Analyses

Aim 1 Analyses

The primary outcomes are continuous and will be ascertained at the planned baseline and follow-up assessment (3 months) from administrative data collected from the EHR on all eligible LBP Veterans presenting at participating clinics. Changes in pain interference and/or physical function scores will be estimated and the primary hypotheses tested via hierarchical linear mixed-effects models with patients nested within clinics and baseline and 3 month values in the response vector.⁵⁵ Hierarchical linear models are a flexible and powerful analytic tool for clustered longitudinal continuous outcomes. The fixed-effect portion of the model will have the form: $Y_{ijk} = \beta_0 + \beta_1 * (followup) + \beta_2 * (followup * intervention)$ for clinic i , patient j , at time k . Random effects (clinics and time by clinics) will be included in the model to account for clustering of patients within clinics as the clinics are the unit of randomization, random effects will also be included to account for the within-patient correlation between repeated measures over time. We will assess the best fitting random effects structure by fitting a variety of random coefficient models (e.g., random intercept only, random intercept and linear slope) and assess using Akaike Information Criteria (AIC) model selection criteria.^{56,57} The predictors in the model will include a time effect and indicator variables for treatment interacting with the time effect. The intraclass correlation capturing the relationship of outcomes between patients seen at the same clinic is accounted for via the random effects for the clinics and time by clinics, which are assumed to be normally distributed. The model will be fit in the SAS procedure PROC MIXED using full likelihood approximation and the hypotheses will be tested by whether the estimated coefficient β_2 is positive and significantly different than 0 at the 0.025 level due to 2 primary outcome variables. We will include covariates used in the covariate constrained randomization⁴ (5 potential variables; average pain scores, clinic location (main medical center/community clinic), number of participating primary care providers, average level of opioid exposure of LBP patients at clinic, and average age of LBP patients at clinic) in our primary model as well as a limited number of patient-level covariates that are readily available in the EHR (age, gender, race and a comorbidity measure). While we have procedures in place to monitor timing of the 3-month follow-up assessment in the EHR, if we have a significant number of assessments outside the 1-month window for the 3-month assessment that are dropped from the primary analysis, we will conduct a sensitivity analysis including the assessments outside the window and estimating a 3-month treatment effect from this model.

Secondary Analyses

We will assess differences in proportions of “responders” between treatment arms for each of the primary outcomes. A “responder” will be defined as achieving 30% improvement in pain interference or function scores at 3 months follow up.⁵⁸ Responder status for those missing outcome data will be estimated using best linear unbiased predictors from the hierarchical linear model⁵⁹ so that those missing observed follow up data will be included.

We will use a generalized linear mixed model with a logit link function to compare differences in responder status between arms where the main predictor of interest will be treatment arm adjusting for clustering of VA clinic either with random effects or by conditioning.^{55,60,61} As a sensitivity analysis to explore responder cut points of pain interference and function measures, we will compute cumulative proportion responder analysis graphs.⁶²

Secondary outcomes of sleep, opioid use, and health utilization (including chronic opioid usage) will also be obtained administratively on all eligible subjects. The sleep PROMIS measure is a continuous outcome that will be assessed at baseline and 3 months and similar modeling procedures as described for the primary outcomes will be used. Opioid use will be examined in two ways, one as a binary variable based on whether a chronic opioid user or not at baseline and 12 months and second using a continuous measure of morphine equivalents for opioid dose at baseline and 12 months.⁶³ For the dichotomous outcomes, we will use a generalized linear mixed model with a logit link function where the main predictor of interest will be treatment arm and will include baseline opioid use status (chronic or not chronic) adjusting for clustering of VA clinic either with random effects or by conditioning.^{55,60,61} For opioid morphine equivalent dose, we will fit a similar model as was described for the primary outcomes except the follow up time point in the model will be for 12 months. For imaging and ED utilization, we will assume a count-like distribution for the number of ED visits in the 12 months of follow up and will use generalized linear mixed model for count variables.⁵⁵

The survey outcomes for the enrolled subset of patients will be collected at baseline, 3, 6, 9, and 12 months and will include pain interference, function, intensity, catastrophizing, sleep, and depression (see Section 10 for full descriptions). These are all longitudinal continuous outcomes and a hierarchical linear model similar to that described for the primary aim will be fit. We will fit random coefficient models as described above (e.g. random intercept only, random intercept and linear slope) and assess using AIC model selection criteria to determine best model for the covariance structure. Similarly, we will determine the best model for the mean structure (e.g. linear, quadratic, dummy coding) as there are five outcome measurement occasions guided by descriptive plots and model fit assessed using AIC model selection criteria. Due to the timing of administration of baseline surveys that some baseline surveys may occur after the initial intervention contact, we will conduct sensitivity analysis treating baseline surveys after initial provider contact as occurring in the post-treatment period.

Aim 2 Analyses

As highlighted in the UG3 section we have strong clinical and scientific rationale to investigate chronic vs. acute LBP and previous opioid use vs. opioid naïve as *a priori* subgroups for treatment moderation.³⁸ We will define “chronic low back” as pain that has persisted for at least 3 months and resulted in pain on at least half the days in the past six months to be consistent with the NIH task force definition.⁴⁹ All participants will have chronicity of back pain assessed via the EHR template (see Section 6) at the time of initial referral to a given care pathway using questions specified in the NIH minimum dataset.⁴⁹ Opioid exposure prior to pathway entry will be defined as being prescribed at least one prescription opioid for 20 or more consecutive days (yes or no within 12 months prior to entering pathway).⁶⁴ This definition could be altered if different ones are suggested for use by the PMC3. These data will be obtained through VA’s Pharmacy Benefits Management System.

For the planned subgroup analyses for key moderators on the primary outcomes of pain interference and function will be the same modeling framework as described for AIM 1 with the addition of the indicator variable(s) for the moderator and associated interactions.⁶⁵ The fixed-effect portion of the model will have the form: $Y_{ijk} = \beta_0 +$

$\beta_1^*(\text{moderator}) + \beta_2^*(\text{moderator}^*\text{intervention}) + \beta_3^*(\text{followup}) + \beta_4^*(\text{followup}^*\text{intervention}) + \beta_5^*(\text{moderator}^*\text{followup}) + \beta_6^*(\text{moderator}^*\text{intervention}^*\text{followup})$ for clinic i , patient j , at time k . A random effects (clinics and time by clinics) will be included in the model to account for clustering of patients within clinics, as the clinics are the unit of randomization. Differential change in pain interference or function by moderator for the two intervention groups is supported if the coefficient for β_6 is significantly different than zero at the $p=0.025$ level. For the adherence multinomial outcome, we will fit a generalized linear model with a random effect for clinic and cumulative logit link function. As the adherence outcome is potentially a 3-level outcome there will be two interaction terms to examine for moderation effects (e.g. whether the effect of the intervention by chronicity is different for those moderately adherent vs. not adherent and/or those fully adherent vs. not adherent).

Exploratory analyses to identify multidimensional subgroups from combinations of baseline characteristics (e.g. age, sex, opioid use) for treatment moderation of the primary outcomes of pain and function as well as per protocol adherence to treatment.

Patients are likely to vary in treatment response. This variation is known as heterogeneity of treatment effects (HTE). Exploration of HTE has typically focused on one-factor-at-a-time post-hoc subgroup analyses (as described in our planned subgroup analysis); however, it is possible to instead identify multidimensional subgroups exhibiting HTE. In particular, we will apply the data-driven method GUIDE⁶⁶(Generalized, Unbiased, Interaction Detection and Estimation) that can be used for longitudinal outcomes, so can incorporate all follow-up outcomes at 3 and 12-months, as well as multi-response outcomes. GUIDE uses a regression tree algorithm that identifies subgroups with heterogeneous effects and estimates how the treatment effect varies across the subgroups. We will include baseline demographic (e.g. age, sex, race) and clinical characteristics (e.g. LBP chronicity, opioid use, comorbid conditions) that are available from EHR. GUIDE provides bootstrap confidence intervals for the treatment effects of identified nodes and is available via a software package.

We will also examine “adherence” among all patients referred to one of the clinical pathways. We define “adherence” according to participant participation in planned sessions with intervention team personnel (telephone or in-person) in each care pathway. The number of planned sessions will vary between and within arms (e.g. depending on response to 1st service in pain navigator arm and depending on risk stratification in integrated pathway arm); therefore, we will define adherence as follows: 1) non-adherent – attended no planned sessions 2) partially adherent – attended some, but not all planned sessions 3) attended all planned sessions. Depending on the number of planned sessions in each pathway we will explore additional multi-level variables that may be more informative; structure of the adherence variable for Aim 2 analyses will depend on data distribution.

We will describe adherence in both care pathways in order to identify patient characteristics potentially associated with program participation and improved pain outcomes. We will not test for differences in adherence rates between pathways as our goal is to gain insight into where to target clinical programs and focus efforts to improve access to and patient engagement with non-pharmacologic pain services. We will also conduct exploratory analyses on alternative definitions of adherence or aspects of intervention receipt. For example, in the pain navigator arm, differentiating based on whether someone actually received one of the recommended services.

Exploratory analyses to identify qualitative interactions that define groups of Veterans that have greater improvement in pain and function with the integrated care pathway versus the care

management program, or greater improvement with care management versus integrated care, or no difference in response

As part of personalized medicine, tailored treatment recommendations are the goal. In this trial, we are offering two different treatments, and we want to explore identifying qualitative interactions that define groups of individuals that have greater improvement with one treatment over the other. We will apply the tree-based method called Qualitative Interaction Trees (QUINT) to identify these subgroups.^{67,68} QUINT is a tree-based clustering method for data obtained from a two-armed trial that identifies three subgroups defined by different baseline characteristics of subjects in the study. QUINT uses a partitioning criterion that is maximized using a sequential partitioning algorithm or a stepwise binary splitting procedure. We will use the R package *quint* and apply to our study data to identify characteristics for Veterans where integrated care pathway treatment results in greater improvement in outcomes than care management pathway, subgroup of Veterans that care management pathway results in greater improvements than integrated care pathway and the subgroup for which improvement does not differ between treatments. We will first construct a summary of each patient's repeated measures profile to characterize the patient's change over time at the primary time point 3-months (i.e., whether or not the patient improved and mean improvement). Empirical Bayes estimates from hierarchical linear models will be used to generate individual-level estimates of mean improvement for each of the primary outcomes. Currently this software only supports continuous outcomes so we would not be able to apply to the multilevel response adherence outcome; however, we will monitor updates for expansion to other distributions of outcomes. Limitation of this methods are that subjects with missing data on any included variables are omitted from the analysis, the effect of clustering within clinics is not addressed, and categorical baseline characteristics of more than two categories cannot be used.

Statistical methods for heterogeneity of treatment effects (HTE) are a rapidly developing field. We will monitor the development of new methods that may be applicable to our study for adapting the analysis plan for this aim, and work closely with the PMC3 Biostatistics Working Group and [name] (an internal advisory member for this proposal) to ensure robustness of our chosen methods.

Missing Data. We do not anticipate much missing data in the main predictors of interest, intervention arm and patient characteristics available in the EHR or assessed at baseline in survey outcomes. There may be missing values in the outcome measures due to dropout, death, a missed interim assessment or assessment outside 1-month window for 3-month follow-up, or item non-response. However, hierarchical linear mixed models via maximum likelihood estimation, our main analysis technique for the primary outcomes, implicitly accommodate missingness at random (MAR).⁵⁵ Therefore, inferences will be valid even with differential dropout by intervention arm. We will thoroughly explore reasons for dropout, and depending upon the type and scope of missing data, we may explore the sensitivity of intervention effects to different missing data mechanisms (MAR vs. MNAR).⁶⁹ Our plan would be to conduct sensitivity analyses to evaluate the sensitivity of the assumption of MAR and/or MNAR on intervention effects. If our primary model included design variables only (treatment, stratification variables, clinic) this model would meet the MAR assumptions if missing data is related to previous outcome assessments or design variables included in the primary model. We can assess the sensitivity of the MAR assumption by conducting an analysis that includes auxiliary variables (either as additional variables in primary models or by conducting a multiple imputation including auxiliary variables). These auxiliary variables or other baseline characteristics for the large sample may be limited due to availability in the EHR. We are currently proposing to include age,

sex, race, and a comorbidity index in our primary analysis that may strengthen our MAR assumption. To explore the MAR assumption, outcomes will be multiply imputed using principled methods in SAS (via PROC MI or IVEware).⁷⁰ Multiple imputation provides a framework for being able to incorporate information from important auxiliary variables while still preserving a parsimonious main treatment effect model and is described as a significant advantage in recommendations from Panel on Handling Missing Data in Clinical Trials.⁷¹ Note that if needed, we will utilize imputation methods that account for the multiple levels of correlation inherent in the clustered data structure. If we cannot justify the assumption of MAR, we will explore the sensitivity of intervention effects to the MNAR assumption; we will follow guidelines in Mallinckrodt⁷² and Ratitch et al⁶⁹ for model selection and pattern mixture modeling.

